1. INTRODUCTION

1.1 BACKGROUND

Poor cognitive function is a serious problem in the aging HIV-positive population. It has been estimated that 52-59% of adults with HIV have cognitive impairment.^{1,2} Such cognitive impairments are known to interfere with medication adherence, compliance to medical appointments, emotional well-being, and everyday functioning (i.e., driving and financial management).³⁻⁷ The source of this cognitive impairment appears to stem from both the viral infection as well as from the agents used to treat the disease. For instance, even though HIV replication may be hindered with antiretroviral therapy (HAART), HIV continues to produce neuro-inflammatory proteins (e.g., TAT, gp120); likewise, some HAART medications may produce metabolic and neurotoxic effects that reduce brain reserve (i.e., the brain's ability to cope with impairment while maintaining functionality)⁷. For example, HIV positive individuals prescribed HAART demonstrate reduced *N*-acetylaspartate (NAA) and decreased levels of NAA in persons prescribed HAART are associated with brain mitochondrial toxicity,⁸ and reduced brain energy metabolism. Although the cause for cognitive decline commonly observed in the HIV positive population is not entirely clear, it is likely linked to inflammation and/or deficits in available energy. Thus, treatments that address inflammation and brain energy metabolism may prove beneficial for prevention or reversal of cognitive decline in the aging HIV-positive population.

One such treatment is a ketogenic diet (KD) (i.e. < 50 grams of dietary carbohydrate (CHO)/day). In the absence of available CHO, the body burns fat as a fuel, which creates ketones as a by-product. Ketones are a highly efficient metabolic fuel readily used by the brain.⁹ While the precise mechanisms are unclear, KDs have been associated with improved brain fuel metabolism, neural antioxidant effects, reduced expression of crucial genes involved in inflammation, greater adenosine triphosphate (ATP) production, and increased mitochondrial biogenesis in animals^{10,11} and humans.^{12,13} More importantly, these physiological adaptations have been linked to improved cognitive function in other neurological disorders (i.e., Alzheimer's¹³ and Parkinson's disease,¹⁴ *amyotrophic lateral sclerosis (ALS)*,¹⁵ and epilepsy)^{12,16} and have enhanced memory improvement in older adults with pre-existing mild cognitive impairment.¹⁷ While the metabolic and neurologic benefits of a KD are well documented in some populations,¹⁸ the neurocognitive, inflammatory, or cardiometabolic effects of a KD in medically stable older HIV patients have not been explored. *This study will address these gaps.*

2. 1.2 PRECLINICAL DATA. N/A

3. 1.3 CLINICAL DATA TO DATE

[figure not shown]
To our knowledge, this is the first study to examine the effects of a Ketogenic Diet in an HIV human population. However, animal studies support the potential cognitive benefit of a ketogenic diet in the context of HIV infection.

2. STUDY OBJECTIVES

In medically stable, older (> 50 years) HIV patients with cognitive impairment, this study will:
Test the feasibility of recruitment, retention, and adherence to a ketogenic diet versus patient choice diet (PCD) intervention.

2.1 Primary: Compare the impact of a 12-week KD versus PCD on:

1. 2.1.1 Cognitive function (*at 12 weeks*).
 2. 2.1.2 Inflammation (*at 12 weeks*).
 3. 2.1.3 Cardiometabolic profile (*at 12 weeks*).
 4. 2.1.4 Persistence of cognitive effects (*at 18 weeks*).
3. STUDY DESIGN: Randomized, 2-group pre/post design. Participants randomized using permuted block randomization using an algorithm developed by the UAB Center for Clinical and Translational Science Biostatistics, Epidemiology, & Research Design (BERD) team. Due to the nature of the intervention (diet) it isn't possible for participants/study personnel to be blinded.

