5 STUDY PROCEDURES

Following IRB approval and informed consent, eligible participants randomized to either the experimental ($n = 7$) or control group ($n = 7$) and scheduled for baseline data collection. Laboratory, demographic, and anthropometric assessments were completed UAB's Clinical Research Unit (CRU). Baseline data: demographic questionnaire, oral glucose tolerance test (OGTT), inflammatory assays and lipid panel as well as an anthropometric evaluation. Even though all snacks and meals for the KD group provided, KD group participants also provided nutritional counseling specific to the KD as well as provided with handouts. Food selected from an 8-day menu. Meals matched for energy content to maintain current energy balance (eucaloric) consisting of < 50 grams CHO/day. Daily CHO intake primarily derived from fresh vegetables.

After laboratory assay and body composition assessments collected, questionnaires and cognitive testing in a private conference room away from outside distractions completed. Delivery of meals/snacks (week 1) to begin the week following baseline data collection.

Food delivery via courier on the same day of the week across the study. All frozen/refrigerated items delivered in a commercial grade cooler. All items clearly labeled with easy-to-understand preparation instructions.

Data Collection

Data collection in the UAB Clinical Research Unit after a 12-hour fast collected by registered nurses well-versed in research methodology. Data collection described below. **Data collection collected at baseline**

and week 12 unless otherwise stated. **NOTE: Cognitive assessments completed at baseline, week 12, and week 18.**

Demographics (baseline only): Age, education, gender, marital/partner status, employment status/disability eligibility, SES (Medicaid, food stamps, public housing eligibility), years since HIV diagnosis (baseline only).

[figure not shown]
Anthropometrics: Height, weight, BMI, waist and hip circumference (baseline/week 12). Height (nearest 0.1 cm), waist circumference (nearest 0.1 cm), and hip circumference (nearest 0.1 cm) measured with Gulick tape measure. Weight (nearest .01 kg) assessed using a Tanita body composition analyzer BC418, Tanita Corp of America, Arlington Heights, IL. BMI calculated.²³ Waist circumference measured at the umbilicus at end of inspiration. Hip measures evaluated at widest hip portion.

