short in duration. In addition, there are no known lasting testing anxiety effects in older populations.

Diet: Those randomized to the KD may experience normal transient reactions such as hunger, weakness, lightheadedness, constipation, fatigue, dizziness, or cravings for certain foods during the first few days of the

KD; however, these effects are mild in nature and resolve without intervention as the body adapts to the new diet. No known long-term risks associated with KD. The most common adverse effects are constipation

(prevalence ~30%), loss of energy (prevalence ~35-37% and bad breath (prevalence ~ 43%), all of which resolve within few weeks as the body adapts to the new diet. Daily energy intake eucaloric (weight maintaining) so changes in weight not anticipated.

Inquiry regarding adverse effects assessed by project coordinator at week 4, week 8, and week 12. Study physician notified immediately for serious adverse effect. In addition, documentation submitted to the IRB

submitted within three business days after any adverse effect reported. Medical monitoring conducted by

primary investigator in collaboration with the study physician. Monitoring completed by registered nurses

during data collection in the Clinical Research Unit.

All testing will be performed by trained personnel, blood samples will be collected by registered nurses, and all equipment will be calibrated daily before testing. Prior to giving consent, all potential participants will be allowed to see equipment and facilities. If an individual indicates discomfort or the desire to discontinue testing, tests will be terminated immediately.

During routine visits and telephone calls, the study coordinator will query participants for any adverse events since their last contact with study personnel. In the case of an adverse event during times of testing, a study physician will be on call. A medical doctor will provide medical supervision for this study. All adverse events will be reported to the UAB IRB and reviewed by the investigative team. Should any of these individuals and/or the IRB identify that any adverse event may be related to the study protocol, testing will be suspended and the protocol will be amended accordingly.

Transient testing fatigue is likely to occur by the end of data collection on weeks 1 and 12; however, the fatigue will be minimized by the provision of a 45-minute break and a meal following the OGGT.

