8 DATA HANDLING AND RECORD KEEPING CONFIDENTIALITY

Loss of confidentiality: Participant information kept confidential to the extent allowed by law. However, research information that identifies an individual may be shared with the UAB Institutional Review Board (IRB) and others who are responsible for ensuring compliance with laws and regulations related to research, including people on behalf of the Center for AIDS Research and the Office for Human Research Protections (OHRP). Inform participants that results of the treatment may be published for scientific purposes; however individual identifies will not be disclosed. Participants will be assigned

a study ID number, which will be used for identification of data collected. No personal identifiers on any data beyond the demographic sheet will be included. As such, the demographic sheet is the single study identifier with corresponding participant name. The demographic questionnaire will be secured in a locked cabinet in the PI's locked office until participant data collection complete and data are entered. Data entry into a Redcap database will only occur on a secure computer under direct supervision of the project coordinator or PI. Only study staff approved on the IRB protocol will have access to the database.

Source Documents & Records Retention

A chart will be created for each participant after consent. During study participants, charts will be maintained in the project coordinator's office located in the Center for Clinical and Translational Sciences in

7 a secure cabinet in a locked office. After study completion, charts will be maintained in the PIs locked office

cabinet located in a secure building requiring approved access to enter for seven years.

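### The diet rationale for not blinding does not cover cognitive testers, scorers or the analyst, and the plan describes no masked assessment

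*Combined protocol and SAP*

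**What the plan says.** Section 3 (Study Design) gives the only statement on blinding: because the intervention is a diet, it is not "possible for participants/study personnel to be blinded". It makes no exception for outcome assessment or analysis, and no other section mentions either.

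Section 2.1 reads "Compare the impact of a 12-week KD versus PCD on" a list that begins with cognitive function at 12 weeks (2.1.1) and ends with persistence of cognitive effects at 18 weeks (2.1.4). Section 5 describes the battery. Trails A and B and Stroop are scored on time. Digit Symbol and the Hopkins delayed recall are counts of correct responses, and Digit Span and the Hopkins learning trials depend on recalled items.

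On who does what, the documents are brief:
- Section 5: data are "collected by registered nurses well-versed in research methodology", food goes out by courier, and cognitive testing follows in a private room.
- Section 7: "All testing will be performed by trained personnel". The project coordinator asks about adverse effects.
- Section 8: each participant receives "a study ID number, which will be used for identification of data collected", and only the demographic sheet links it to a name.

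Section 5 also has participants randomized "and scheduled for baseline data collection", in that order.

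**The concern.** The reason given is narrower than the conclusion drawn from it. People who eat, deliver or counsel on a diet cannot be masked to it. Someone who holds the stopwatch, marks a recall sheet or runs the ANCOVA need not know the group.

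The tests are administered by a person, so timing, prompting and scoring by an examiner is the natural reading, although the text does not say so. An examiner who knows the group and expects the ketogenic diet to help can shift scores in one direction. Because randomization is listed before baseline testing, the group could be known at all three cognitive assessments.

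Section 6 names feasibility and effect-size estimation as the pilot's purpose. A systematic shift enters that estimate, and a larger later trial does not correct a planning value that was biased from the start.

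**Working it through.** The plan states no figure on this point, so there is none to reproduce. The first step is a comparison of roles with the reason given; the second is an illustration of scale.

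**Step 1: does the diet rationale reach each role?**

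| Role | Reached by the diet rationale? | What the documents say |
|---|---|---|
| Participants | Yes | Not blinded |
| Food delivery and counselling staff | Yes | Courier delivers; counsellor not named |
| Cognitive tester | Not by itself | Not named |
| Scorer | No | Not named; data carry a study ID |
| Analyst | No | Not named |

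The section 3 sentence treats all five alike.

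**Step 2: illustration of scale.**

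Inputs from the documents: 7 per arm (section 5); ANCOVA of change on group and baseline (section 6), so residual df = 14 − 3 = 11 if all complete.

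Inputs that are assumptions: two-sided alpha 0.05; no true diet effect; a shift *b* in SD units favouring the ketogenic diet at week 12 and absent at baseline; baseline to week-12 correlation *r*; that the impairment score in section 6 draws on the tests above; negligible chance imbalance at baseline.

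Adjustment for baseline reduces the residual SD to √(1 − r²). The noncentrality is δ = [b / √(1 − r²)] × √(n/2), with √(7/2) = 1.871. The critical value of t on 11 df is 2.201. The chance of p < 0.05 is the probability that a noncentral t with df 11 and noncentrality δ lies beyond ±2.201.

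| b (SD) | r | √(1 − r²) | δ | Chance of p < 0.05 |
|---|---|---|---|---|
| 0 | any | – | 0 | 0.050 |
| 0.1 | 0.5 | 0.866 | 0.216 | 0.0545 |
| 0.1 | 0.8 | 0.600 | 0.312 | 0.0594 |
| 0.2 | 0.5 | 0.866 | 0.432 | 0.0681 |
| 0.2 | 0.8 | 0.600 | 0.624 | 0.0881 |
| 0.5 | 0.5 | 0.866 | 1.080 | 0.1671 |
| 0.5 | 0.8 | 0.600 | 1.559 | 0.2965 |

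For comparison, random error: the 95% confidence interval half-width is 2.201 × √(2/7) × √(1 − r²), which is 1.18 SD at r = 0, 1.02 SD at r = 0.5 and 0.71 SD at r = 0.8.

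If the same shift were also present at baseline, the ANCOVA would absorb part of it. With equal SDs, b(1 − r) remains; for example, 0.5 × (1 − 0.5) = 0.25 SD. The week-18 analysis adjusts for the week-12 score, which is itself exposed, so the table does not carry over to objective 2.1.4.

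**The case against.** The strongest reply is that masking may be harder than it looks and may achieve only part of what is hoped. Much of this stands.

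- The cognitive tester is never identified and could be the coordinator or the investigator. Section 7 also has the nurses doing monitoring during data collection, and provides a meal at the week 1 and week 12 visits that could reveal the group.
- Participants stay unblinded. Trails, Digit Symbol and recall depend on effort, so their own expectation remains a source of bias that masked testers cannot remove.
- The pilot is described as hypothesis generating. At 7 per arm, random error is larger than any shift considered here, and a false-positive rate is not the most relevant measure. Bias in the estimate still matters, because it does not average out.

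A reader might infer more than the documents support:

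- *That masking would cost nothing in staffing.* The documents give neither staff numbers nor the tester's other duties.
- *That the coordinator handles diet contact and the testers are therefore separate.* The coordinator is assigned adverse-effect inquiry and shared supervision of data entry; who counsels is not stated.
- *That testing is in fact done unmasked.* This is a fair inference from the section 3 sentence, but nothing describes the testing itself in those terms.
- *That the laboratory outcomes are equally exposed.* They are assay- or analyser-based, and nothing says laboratory staff know the group.
- *That the false-positive rate is 30%.* That is the extreme corner of an assumed range; at 0.1 SD the effect is negligible.

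**Conclusion.** The point holds in limited form. The stated reason does not justify leaving testers, scorers and the analyst unmasked, and the plan provides no masked assessment for the cognitive tests that serve primary objectives 2.1.1 and 2.1.4.

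Its size cannot be established from the documents. Under the assumptions listed, the chance of a false positive is about 5-6% for a 0.1 SD shift and about 7-30% for 0.2 to 0.5 SD with correlation 0.5 to 0.8. These figures are illustrative and describe the whole assumed shift, not the part that masking would remove.

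I am confident in the gap in the text, and less so in how fully masking can be achieved with the staff available. It is a low-cost improvement that should be made, not a flaw that invalidates the pilot.

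**What to change.** Replace the blinding sentence in section 3 with text to this effect:

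- Participants and staff who deliver the diet or counselling are not blinded.
- Where existing staffing allows, cognitive testing at all three assessments is done by personnel who have no diet contact, take no part in adverse-effect inquiry and are not told the group.
- Participants are asked not to mention their diet to the tester.
- Test forms are scored from ID-coded sheets.
- The analyst works with a coded group variable until data lock.

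If the only available tester also has diet contact, say so as a limitation and keep the masked scoring and coded analysis, which do not depend on who tests.

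The cost is protocol wording and some scheduling constraint for 14 participants and three cognitive assessments; the sample size stays at 7 per arm. Some unmasking through participants or the on-site meal should be expected. The report should state that participant expectation was not controlled.

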4. SUBJECT SELECTION

4.1

4.2

4.3

INCLUSION CRITERIA

> 50 years with stable HIV and cognitive impairment as determined by the Modified Telephone Interview for Cognitive Status (TICS-M) Scale. Participants required to have stable HIV infection as evidenced by CD4+ lymphocyte count > 350 cells/mm³ for at least two years and prescribed their current cART regimen for at least six months.

EXCLUSION CRITERIA

Current drug or alcohol abuse (> 3 drinks/day), past medical history of mental disorders (i.e., schizophrenia, bipolar), neural injury (i.e., cerebral vascular accident or traumatic brain injury), dementia, Parkinson's, diabetes mellitus, hearing impaired, or any other condition that contraindicates participation.

SUBJECT RECRUITMENT AND SCREENING

Participants recruited from the UAB 1917 HIV/AIDS Clinic using fliers within the clinic as well as by advertisement on a rolling kiosk located in the clinic lobby.

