6. STATISTICAL PLAN

Sample Size. Feasibility and preliminary data for effect size estimation is the primary purpose of this pilot

study (hypothesis generating).

Descriptive analyses.

Demographic, Anthropometric and Baseline Characteristics: Demographic data (i.e., age, education, gender, marital/partner status, employment status, and years since HIV diagnosis) were evaluated using frequencies and reported for each group. Ratio/interval data (i.e., anthropometrics (i.e., height, weight, BMI, waist and hip circumference, cognitive performance by instrument; inflammatory markers (CRP, TNF-a, IFNy, IL-1B, IL-6, IL-8, and IL-12p70); cardiometabolic factors (OGTT, glucose, C-peptide, and insulin) reported via mean/SD at baseline by group. Between-group t-tests will explore group differences at baseline.

Primary analysis: All the primary outcomes (impairment score, inflammatory markers and cardiometabolic factors) will be examined by an analysis of covariance (ANCOVA) including the change from baseline to completion of diet treatment as dependent variable, study group as independent variable, and baseline measures as a covariate, to evaluate the effects of a 12 week KD versus PCD. The lasting cognitive effects of a 12-week KD versus PCD six weeks post intervention completion was determined by an ANCOVA including the change of impairment score from 12 week to 18 week as dependent variable, study group as independent variable, and impairment score at 12 weeks as a covariate.

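### People already eating below 50 g carbohydrate a day are eligible, and the visible plan does not record whether PCD participants start a KD, so the week-12 difference could be diluted without anyone knowing

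*Combined protocol and SAP*

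**What the plan says.** Section 1.1 sets the level that defines the test diet: "One such treatment is a ketogenic diet (KD) (i.e. < 50 grams of dietary carbohydrate (CHO)/day".

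Section 4 selects on age, stable HIV, antiretroviral regimen and cognition: "> 50 years with stable HIV and cognitive impairment as determined by the Modified Telephone Interview for Cognitive Status (TICS-M) Scale". Its exclusions are substance abuse and medical, psychiatric, neurological and hearing conditions, closing with "diabetes mellitus, hearing impaired, or any other condition that contraindicates participation". Usual diet and carbohydrate intake are not mentioned. Recruitment is by advertisement in the clinic, "using fliers within the clinic as well as by advertisement on a rolling kiosk located in the clinic lobby".

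The comparator appears in Section 2 only by name, in the feasibility aim on "adherence to a ketogenic diet versus patient choice diet (PCD) intervention". Section 5 randomises seven people to each arm and describes food and counselling for one of them: "Even though all snacks and meals for the KD group provided, KD group participants also provided nutritional counseling specific to the KD". It lists no food record, carbohydrate intake or ketone measurement for either arm. Section 7 has the project coordinator ask about adverse effects at weeks 4, 8 and 12, with no question on diet.

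Section 3 states that participants and staff cannot be blinded. Section 6 gives the purpose: "Feasibility and preliminary data for effect size estimation is the primary purpose of this pilot". Its primary analysis is an ANCOVA of the change from baseline to the end of the diet period, with group and the baseline value as terms. The week-18 analysis takes the change from week 12 to week 18, adjusted for the week-12 score.

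**The concern.** The quantity the pilot should deliver is an effect size for a change to a KD compared with no such change. Two kinds of participant carry no contrast. One enters already on a KD and is randomised to KD. The other is randomised to PCD and starts a KD during the study. Section 4 admits the first, and nothing in the visible procedures would reveal the second.

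The second is possible because the trial is open, participants answer advertisements, and they are selected for a cognitive problem that the diet is hoped to help. With seven per arm, one person is a seventh of the arm.

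The harm falls mainly on the estimate. If some participants had no contrast and nobody recorded it, a later trial planned on the result would start from an understated effect and could not correct it. The ANCOVA adjusts only for the baseline value of the outcome, so it cannot identify these people.

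**Working it through.** There is no stated figure to reproduce. The seven per arm in Section 5 come without an alpha, power, effect size or SD.

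**Inputs.** n = 7 per arm (Section 5). KD means below 50 g carbohydrate a day (Section 1.1). The outcome is change from baseline to week 12 (Section 6). Assumption: moving to a KD shifts the outcome by the same amount δ in everyone. All frequencies below are assumptions, because the documents give none.

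**Step 1: who dilutes the week-12 comparison.** Consider the diet-driven change each person contributes.

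| Participant | Expected contribution | Actual contribution | Loss of contrast |
|---|---|---|---|
| Habitual KD eater, KD arm | δ | 0 | δ/7 |
| New KD adopter, PCD arm | 0 | δ | δ/7 |
| Stable habitual KD eater, PCD arm | 0 | 0 | none |

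The third row follows from analysing change: that person's diet does not change, as with any other control. The table is exact for simple change from baseline. Adjusting for baseline makes the split of the loss between the two kinds of habitual eater approximate, but not their expected total over randomisation.

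**Step 2: size per person.** With k such people in one arm, the retained fraction is f = 1 − k/7, and the sample size needed for the same precision relative to the effect grows by 1/f².

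- k = 1: f = 6/7 = 0.857, a loss of 14%; 1/f² = 1.36
- k = 2: f = 5/7 = 0.714, a loss of 29%; 1/f² = 1.96

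The inflation factors only convey scale, since the plan has no sample-size calculation for them to act on.

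**Step 3: size against the noise.** Ignoring any gain from the covariate, the standard error of the difference is √(2/7) = 0.53 SD.

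- Assumed effect 0.8 SD: shift per person 0.8/7 = 0.11 SD, and 0.11/0.53 is about 0.2 standard errors
- Assumed effect 1.5 SD: shift per person 1.5/7 = 0.21 SD, and 0.21/0.53 is about 0.4 standard errors

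**Step 4: how likely.** If a share p of eligible people already eat a KD, the chance of at least one in the KD arm is 1 − (1 − p)⁷. If a share c of the remaining PCD participants adopt one, the expected retained fraction is f = (1 − p)(1 − c).

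| Assumed p | At least one in KD arm | f, c = 0 | f, c = 10% |
|---|---|---|---|
| 5% | 30% | 0.95 | 0.86 |
| 10% | 52% | 0.90 | 0.81 |
| 20% | 79% | 0.80 | 0.72 |

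At p = 2%, the chance of at least one is 13% and the retained fraction without adopters is 0.98.

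**Step 5: week 18.** The dependent variable is the change from week 12 to week 18. A PCD participant who adopted a KD before week 12 and stays on it has no diet change in that window. One who starts after week 12 does. The effect on the comparison depends on timing and on what the KD arm eats after week 12, so the 1/7 figure does not carry over.

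**The case against.** Several objections have force.

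- **The frequency is unknown and may be nil.** Keeping below 50 g a day without the meals, delivery and counselling given to the KD arm is demanding. This stands: the documents support a risk only.
- **The shift is small beside the noise.** At 0.2 to 0.4 standard errors per person it would be hard to see in 14 people. A reader might infer that a true effect could be discarded, but the plan sets no power target or go/no-go rule, so that does not follow. The shift is nevertheless a bias in the estimate the pilot exists to produce, and recording diet is the only way to know of it.
- **Patient choice is a legitimate comparator.** A provided KD against whatever patients choose is a fair question, and under it a PCD participant who chooses a KD is an ordinary control. This stands. A reader might infer that the comparator is faulty or that PCD participants must be told to avoid a KD. The documents do not support that, and such a rule would change the question asked.
- **An instruction or diet measure may exist elsewhere.** Consent pages and some figures are not available. The point is therefore limited to the visible criteria, procedures and analysis.

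Two further readings are tempting. One is that anyone already on a low-carbohydrate diet removes the contrast in either arm. A stable KD eater in PCD behaves like other controls in a change analysis, and a diet above 50 g a day reduces the contrast without abolishing it. The other is that the week-18 result is also pulled toward zero, which the planned week-12-to-18 change does not imply.

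**Conclusion.** The gap is real and narrow. Section 4 admits people who already eat at the protocol's KD level, and the visible plan would not show whether PCD participants start a KD. Under a uniform effect, each habitual KD eater in the KD arm, or each new adopter in the PCD arm, would remove about 14% of the expected week-12 difference in change from baseline. The conclusion rests on that assumption and on such people enrolling, for which the documents give no rate. It does not extend to stable KD eaters in the PCD arm or to a stated direction of bias at week 18. What is at stake is the accuracy of the pilot's effect-size estimate.

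**What to change.** 1. Add to Section 4 an exclusion for people currently eating a ketogenic diet, taken as below the protocol's own 50 g carbohydrate a day, asked at screening alongside the TICS-M.
2. Add to the coordinator's existing contacts at weeks 4, 8 and 12, and to the week-18 visit, a yes/no item on whether a PCD participant has started a KD.
3. State in Section 6 that everyone stays in the arm as randomised, that the count is reported by arm, and that the effect-size estimate is interpreted in light of it.

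The cost is one screening question and one item at contacts already planned. A few otherwise eligible people would be excluded, and both items rely on self-report. Whether PCD participants are asked not to start a KD is the sponsor's choice of comparator and is not part of this change.
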